5.5 Measures to minimize/avoid bias

The trial is open-label. Despite the obvious benefits of a double-blind design, the indication to proceed with angiography-derived FFR or not cannot be concealed to the operator nor to the patient. An independent Clinical Event Committee (CEC) will adjudicate all endpoints. The CEC members and the CEC management team will be completely blinded to the randomization, as well as patient identifying information. The CEC will adjudicate the events based on pre-determined definitions outlined below. Other measures to avoid or minimize bias introduced by the open-label design will include intent-to-treat principles of analysis and use of objective measures for endpoint classification.

6 STUDY POPULATION

6.1 Inclusion criteria

1. STEMI with indication to invasive management **AND**
2. Multi-vessel disease defined as at least 1 non-culprit coronary artery lesion at least 2.5 mm in diameter deemed at visual estimation with a diameter stenosis % ranging from 50 to 99% amenable to successful treatment with PCI **AND**
3. Successful treatment of culprit lesion

6.2 Exclusion criteria

1. Planned surgical revascularization
2. Left main as non-culprit lesion
3. Non-cardiovascular co-morbidity reducing life expectancy to < 1 year
4. Any factor precluding 1-year follow-up
5. Prior Coronary Artery Bypass Graft (CABG) Surgery
6. Impossibility to identify a clear culprit lesion
7. Presence of a chronic total occlusion (CTO)

7 STUDY PROCEDURES

7.1 General information regarding revascularization

Second generation drug eluting stents (DES) must be implanted. All patients must be treated with low dose ASA and a P2Y12 inhibitor (ticagrelor or prasugrel unless contraindicated). The use of a glycoprotein IIb/IIIa inhibitor is left to the discretion of the operator. The use of heparin, bivalirudin or low molecular heparin for procedural anticoagulation is also left to the discretion of the investigator. Radial approach is strongly recommended.

7.2 Conventional angiography guided complete revascularization

[figure not shown]
[figure not shown]
All patients randomized to angio-guided revascularization must undergo PCI of all non-culprit lesions angiographically deemed $\geq 50\%$. Complete revascularization must be obtained within index hospitalization.

7.3 Functional coronary angiography complete revascularization

Patients who are randomized to this strategy will receive revascularization of the culprit lesion and functional coronary angiography evaluation on all non-culprit lesions (angiographically deemed $\geq 50\%$) and revascularization of all-functional positive lesions according to angio-FFR based virtual PCI plan. Functional evaluation is mandatory for all stenosis. When angiography-derived FFR is not feasible with any of the available tools, then a staged procedure to perform invasive FFR is mandatory. According to available literature, the overall rate of invasive FFR should not exceed 5% of the patients. PCI of vessel with negative functional evaluation is considered a protocol violation. Revascularization of the positive (at angiography-derived FFR assessment) non-culprit lesions must be performed within the index hospitalization.

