2.9 Novel angiographic measures of plaque composition and vulnerability

Different methods aimed at the estimation of plaque composition and vulnerability have been developed. They are all based on analyses performed on angiography.

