7.3.1.2 Angiography-derived measurement of plaque vulnerability

In patients randomized to the AIR strategy with negative FFR, a further stratification of NCLs will be performed. Vessels with an angiography-derived measurement of plaque vulnerability above the validate thresholds (RWSmax >12% or TSVI $\geq 40.5 \text{ m}^{-1}$) will receive PCI whereas those below the threshold will be treated with optimal medical therapy (OMT).

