7.4 Index coronary angiography and functional assessment

The initial angiogram and PCI for the index and eventual staged CAA and PCI in all patients should be recorded, anonymized and maintained locally for shipment to the angiographic and functional core lab (CD, DVD or digital files are acceptable). Regarding the patients randomized to functional coronary angiography complete revascularization (experimental arm), the investigators within 24-48 hours from randomization must send to core lab the recorded and anonymized angiographies of non-culprit vessels. This will allow to the core lab to perform the analysis and to re-send to investigators the report with the indication to proceed or not to revascularization and the eventual procedural plan within 12-24 hours.

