9 STATISTICAL ANALYSIS PLAN

Analysis will be performed on an Intention to Treat (ITT) set, defined as all intentionally randomized patients, by randomization treatment. Supportive per-protocol analyses will be performed on the primary and key secondary endpoints. Correction for multiple testing to account for type I error will be performed according to Holm, and Bretz graphical approaches²⁵.

A detailed statistical analysis plan will be completed before the end of the study. In brief, continuous variables will be tested for normal distribution with the Kolmogorov-Smirnov test and with visual estimate of Q-Q plot. Normally distributed variables will be presented as mean \pm SD and compared by t test and 1-way ANOVA. Otherwise, median [inter-quartile range], Mann-Whitney U and Kruskal-Wallis tests will be used. Categorical variables will be summarized in terms of absolute and relative frequencies (percentages) and compared by using χ^2 test. One-sided tests will be done in order to check the superiority of functionally-driven complete revascularization. Statistical significance will be set at $\alpha=0.05$ level. Formal type-I error control will be ensured for the primary and the secondary endpoint by correction for multiple testing according to Holm, and Bretz graphical approaches²⁵. Kaplan-Meier curves will be plot to describe survival free from adverse events, and difference between groups will be test will log-rank test. The primary analysis will be based on events of all follow-up time of each patient at the time of the database lock. Further analyses will be performed with events after more than 30 days considered as censored, as well as after more than 365 days considered as censored. Any confounding factor will be tested by Cox regression models. Variables with a p-value <0.1 at univariate analysis will be entered into a multivariable analysis to identify the independent predictors. When appropriate, 95% CI will be calculated.

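### Section 7.3 makes PCI of a functionally negative vessel a protocol violation, while its subsection 7.3.1.2 directs that PCI for FFR-negative AIR vessels above the plaque-vulnerability thresholds, with no stated exception

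*Protocol*

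**What the plan says.** Section 7.3 describes the AIR arm. Every non-culprit lesion judged at least 50% stenosed gets a functional evaluation, followed by "revascularization of all-functional positive lesions according to angio-FFR based virtual PCI plan". Where angiography-derived FFR cannot be obtained, invasive FFR is the mandatory fallback. The section then sets its adherence rule: "PCI of vessel with negative functional evaluation is considered a protocol violation". The sentence has no exception and no cross-reference. The one after it reads: "Revascularization of the positive (at angiography-derived FFR assessment) non-culprit lesions must be performed within the index hospitalization".

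Subsection 7.3.1.2 adds a step: "In patients randomized to the AIR strategy with negative FFR, a further stratification of NCLs will be performed". Vessels with RWSmax >12% or TSVI ≥40.5 m⁻¹ "will receive PCI whereas those below the threshold will be treated with optimal medical therapy (OMT").

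Section 9 bases the analysis on the intention-to-treat set and adds: "Supportive per-protocol analyses will be performed on the primary and key secondary endpoints". It leaves the detail to a later statistical analysis plan.

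**The concern.** A rule that defines violations should separate patients treated as the protocol directs from those who were not. Here it does not. An FFR-negative AIR vessel above a vulnerability threshold must be stented under 7.3.1.2, and stenting it is a violation under 7.3.

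Two things are at stake. First, counts of violations in the AIR arm would combine directed PCI with unwarranted stenting of negative lesions, which is the behaviour the rule exists to detect. Second, a per-protocol set built on the violation label would lose correctly treated patients from one arm. That loss would not be random. The patients are selected on plaque vulnerability, and Section 2.9.1 reports that TSVI predicted later myocardial infarction (AUC 0.77), which is a component of the primary endpoint.

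**Working it through.** The protocol gives no figure to reproduce here. The check is a comparison of the text.

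**1. The two rules applied to one vessel.** Take a non-culprit vessel in an AIR patient with negative angiography-derived FFR and RWSmax >12%.

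| Source | Status of the vessel | What follows from PCI |
|---|---|---|
| 7.3 | Negative functional evaluation | PCI is a violation |
| 7.3.1.2 | Negative FFR, above a threshold | PCI is directed |

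**2. Could a high RWSmax or TSVI count as a positive functional evaluation?** If so, the vessel would not be negative and the conflict would vanish. The protocol's usage points the other way:
- Section 7.3 qualifies positive lesions as positive at angiography-derived FFR, and its only fallback is invasive FFR.
- Section 7.3.1.1 requires a virtual PCI plan for every positive functional assessment, aiming at a final angiography-derived FFR ≥0.90. A vessel chosen for vulnerability may already meet that target.
- Section 7.3.1.2 calls the patient FFR-negative before the vulnerability step begins.
- Section 2.9 introduces the new measures separately from the functional assessment: "Different methods aimed at the estimation of plaque composition and vulnerability have been developed".
- Sections 2.8 and 3 present a negative assessment as the reason a patient can avoid a second procedure, with no vulnerability exception.

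**3. Is there an exemption elsewhere?** The synopsis, Sections 2.8, 3, 5.4, 5.5, 7.4, 9 and 12 contain none. The flow chart in Section 5.2 and some other figures are not shown in the text available, so this holds for the visible text only.

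**4. Which arm carries the label?** Section 7.3.1.2 applies to AIR alone. In ANGIO, Section 7.2 requires PCI of every non-culprit lesion of at least 50% stenosis and has no rule about functionally negative vessels. Any mislabelling is therefore one-sided.

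**5. Does it change treatment?** Under Section 7.4 the core lab returns to the investigators "the report with the indication to proceed or not to revascularization and the eventual procedural plan". The operator acts on one indication per case, so the conflict concerns how the PCI is recorded.

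**6. Which analyses depend on the label?** The intention-to-treat set is defined by randomization and does not depend on it. The supportive per-protocol analyses might. This document does not define their set.

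**7. How many patients?** This cannot be computed. The protocol gives no proportion of FFR-negative non-culprit vessels in STEMI that exceed either threshold. The RWSmax and TSVI results in Section 2.9 come from differently selected patients and are not broken down by FFR result.

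**The case against.** The best defence is that a specific rule qualifies a general one. Section 7.3.1.2 sits inside 7.3, and its wording presents a second step after the FFR gate. On that reading 7.3 bars discretionary stenting of negative vessels, and PCI that the protocol itself orders can hardly be a departure from it. This is probably the intent, and it makes the fault one of drafting. It still leaves whoever codes deviations to supply an exemption that 7.3 does not state.

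The wording also differs: 7.3 speaks of a negative functional evaluation, 7.3.1.2 of negative FFR. The phrase tying positivity to angiography-derived FFR stands in the sentence on timing, not in the violation rule. TSVI comes from a flow computation on the same angiographic reconstruction used for the pressure drop (Section 2.9.1), so it could loosely be called functional. That argument is weaker for RWSmax, and step 2 of the check counts against it for both. The reading is not strictly excluded, but it is not the natural one.

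Finally, the per-protocol consequence is conditional. The statistical analysis plan is not at hand and could define the set so that PCI under 7.3.1.2 does no harm. That point stands. It does not repair the violation rule that sites and monitors would apply from the protocol.

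**Conclusion.** The inconsistency is real and should be corrected, but its reach is narrow. As written, the protocol both directs PCI of FFR-negative AIR vessels above a vulnerability threshold and classes it as a violation. The direct effect is on violation reporting in the AIR arm. A one-sided loss from the supportive per-protocol analyses follows only if that set takes the 7.3 label literally. The number affected is unknown.

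A reader might infer more, and the document does not support it:
- **That operators receive opposing instructions.** Section 7.4 gives them one core-lab indication.
- **That the primary result is biased.** The main analysis is by intention to treat and does not use the label.
- **That correctly treated patients will be excluded.** No text says how the per-protocol set is formed.

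The conclusion assumes that functional evaluation in 7.3 means FFR, as the surrounding sections suggest, and that no figure missing from the text states an exemption.

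**What to change.** Add an exception to the end of the violation sentence in Section 7.3: except for vessels meeting the plaque-vulnerability thresholds in 7.3.1.2. State alongside it that PCI performed under 7.3.1.2 is per protocol and is not a reason for exclusion from the per-protocol set.

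The cost is one clause and one sentence in a protocol clarification. The thresholds, the experimental strategy, the endpoints and the sample size stay as they are. Any violations already coded under the literal rule would need to be checked against the core-lab reports and relabelled.

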7.3.1.1 Virtual PCI plan

The virtual PCI plan must be obtained in all patients with positive functional assessment. The aim of the plan is to obtain a final Angiography-derived FFR value ≥ 0.90 . The residual vessel Angiography-derived FFR tool can be utilized to this end.

[figure not shown]
Virtual PCI. Quantitative flow ratio (Angiography-derived FFR) is used as a gatekeeper for percutaneous coronary intervention (PCI). The Angiography-derived FFR analysis shows 1 focal pressure step-down in the distal right coronary artery (RCA). It is possible to plan different treatment strategies (“virtual PCI”) obtaining the “residual vessel Angiography-derived FFR,” which is the Angiography-derived FFR value once the segment between p and d (in green in the Angiography-derived FFR traces) is treated. P and d can be decided and moved by the operator to obtain different post-PCI scenarios. In the example above, residual vessel Angiography-derived FFR would be 0.91 treating lesion 1, resulting in an optimal functional post-PCI result, then confirmed with an actual post-PCI FFR measurement.

7.3.1.2 Angiography-derived measurement of plaque vulnerability

In patients randomized to the AIR strategy with negative FFR, a further stratification of NCLs will be performed. Vessels with an angiography-derived measurement of plaque vulnerability above the validate thresholds (RWSmax >12% or TSVI $\geq 40.5 \text{ m}^{-1}$) will receive PCI whereas those below the threshold will be treated with optimal medical therapy (OMT).

7.4 Index coronary angiography and functional assessment

The initial angiogram and PCI for the index and eventual staged CAA and PCI in all patients should be recorded, anonymized and maintained locally for shipment to the angiographic and functional core lab (CD, DVD or digital files are acceptable). Regarding the patients randomized to functional coronary angiography complete revascularization (experimental arm), the investigators within 24-48 hours from randomization must send to core lab the recorded and anonymized angiographies of non-culprit vessels. This will allow to the core lab to perform the analysis and to re-send to investigators the report with the indication to proceed or not to revascularization and the eventual procedural plan within 12-24 hours.

7.5 Optimal Medical Therapy (OMT)

All patients regardless of randomization group will receive OMT. Unless there is an absolute contraindication, all patients will receive standard secondary prevention with:

1. Aspirin 75-100 mg po daily
2. Ticagrelor 180 mg or Prasugrel 60 mg loading dose then Ticagrelor 90 mg po BID or Prasugrel 10 mg die unless contraindicated. DAPT duration is as for Institutional protocols. In high bleeding risk patients, namely those with one of the following criteria (at least one major or two minor criteria):

Table 3 Major and minor criteria for hbr at the time of PCI

Major	Minor
Anticipated use of long-term oral anticoagulation*	Age ≥ 75 y
Severe or end-stage CKD (eGFR < 30 mL/min)	Moderate CKD (eGFR 30–59 mL/min)
Hemoglobin < 11 g/dL	Hemoglobin 11–12.9 g/dL for men and 11–11.9 g/dL for women
Spontaneous bleeding requiring hospitalization or transfusion in the past 6 mo or at any time, if recurrent	Spontaneous bleeding requiring hospitalization or transfusion within the past 12 mo not meeting the major criterion
Moderate or severe baseline thrombocytopenia [†] (platelet count $< 100 \times 10^9/L$)	Long-term use of oral NSAIDs or steroids
Chronic bleeding diathesis	Any ischemic stroke at any time not meeting the major criterion
Liver cirrhosis with portal hypertension	
Active malignancy [‡] (excluding nonmelanoma skin cancer) within the past 12 mo	
Previous spontaneous ICH (at any time) Previous traumatic ICH within the past 12 mo Presence of a bAVM Moderate or severe ischemic stroke [§] within the past 6 mo	
Nondeferrable major surgery on DAPT	
Recent major surgery or major trauma within 30 d before PCI	

bAVM indicates brain arteriovenous malformation; CKD, chronic kidney disease; DAPT, dual antiplatelet therapy; eGFR, estimated glomerular filtration rate; HBR, high bleeding risk; ICH, intracranial hemorrhage; NSAID, nonsteroidal anti-inflammatory drug; and PCI, percutaneous coronary intervention.
 *This excludes vascular protection doses.⁴²
[†]Baseline thrombocytopenia is defined as thrombocytopenia before PCI.
[‡]Active malignancy is defined as diagnosis within 12 months and/or ongoing requirement for treatment (including surgery, chemotherapy, or radiotherapy).
[§]National Institutes of Health Stroke Scale score ≥ 5 .

Antiplatelet agent choice is left to the Physicians’ discretion and it is mandatory to reduce DAPT duration to 1 month.

3. An ACE inhibitor or ARB appropriately titrated to target a blood pressure of < 130/85. If the patient continues to experience hypertension with BP > 130/85, additional blood pressure lowering treatments should be added: either a thiazide diuretic or dihydropyridine calcium channel blocker. The goal of antihypertensive therapy is to achieve and maintain a target blood pressure (BP) of < 130/85 mm Hg.
4. Statin therapy: Atorvastatin 40-80 mg daily or rosuvastatin 20-40 mg daily or simvastatin 40 mg daily. If, at any time during follow-up, the LDL cholesterol is above the target of 70 mg/dl, the statin dose should be further maximized (if not already attempted). If this still does not result in the desired effect, then ezetimibe can be added. If a patient has a statin related side effect, then, either a lower dose of the same statin or use of a different statin with or without the addition of ezetimibe can be considered. Proprotein convertase subtilisin-kexin type 9 (PCSK9) inhibitors should be utilized to meet the LDL target if otherwise not possible.
5. If the patient is diabetic, the goal is to maintain fasting blood glucose levels between 80-135 mg/dl and hemoglobin A1c levels <7.0%, in accordance with published recommendations of International Guidelines. If these criteria are not met on oral hypoglycemic therapy, then insulin should be strongly considered.
6. If the patient has significant LV dysfunction and heart failure, consideration should be given to administration of an aldosterone antagonist and sodium-glucose Cotransporter-2 (SGLT2) Inhibitors.

7.6 Data collection and Case Report Form

[figure not shown]
The study investigators will be monitored for consecutive recruitment of patients. A registry of excluded patients will be updated monthly and if selection bias is noticed, it would lead to the exclusion of the centre from the investigation. Data will be collected in electronic case report forms (eCRF). The eCRF will be web-based and all investigators will receive specific credentials for the access. The eCRF will also include the web-based tool for randomization. The quality of the data included in the eCRF will be reviewed by the Academic Research Organization (ARO) of the University Hospital of Ferrara. The eCRF will contain a dedicated tool for reporting adverse events.

7.7 Follow-up

After initial hospital discharge, routine clinic follow-up will occur at 1 month \pm 14 days (telephone contact or clinic visit), 1 year (clinic visit) and yearly clinic visits thereafter up to 5 years. At each visit, clinical outcomes, compliance with medical therapy and smoking cessation, will be assessed. LDL, blood pressure and glycemic targets, anginal status (SAQ), quality of life (EQ-5D) will be assessed at the 12-month and 5 year-follow-up visit.

[figure not shown]

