1 STUDY SYNOPSIS

Study Title:	Functional Coronary Angiography to Indicate and Guide Revascularization in STEMI Patients with Multivessel Disease: the AIR-STEMI trial
Protocol version:	V1
Date:	December 9 th , 2022
Study Sponsor:	
Azienda Ospedaliero Universitaria di Ferrara Azienda USL di Bologna Azienda USL-IRCCS di Reggio Emilia, Reggio Emilia, Italy
 
The present trial received the endorsement of the Italian Health Minister that partially supported the conduction of the study with the grant GR-2021-12372516 (Ricerca Finalizzata 2021)

Study Principal Investigator:	[name]
Study Objectives	
The primary aim of the AIR-STEMI trial is to demonstrate the superiority in terms of efficacy of the Angiography-derived FFR strategy (AIR) over that based on conventional angiography (ANGIO). The primary endpoint of the study is the cumulative occurrence of all-cause death, myocardial infarction, cerebrovascular accident, or ischemia-driven revascularization. Secondary efficacy endpoints are the cumulative occurrence of: i) all-cause death, ii) CV death; iii) myocardial infarction, iv) ischemia driven coronary revascularization; iv) Quality Adjusted Life Years (QALYs).
 
The primary safety endpoint of the study is the cumulative occurrence of contrast-associated acute kidney injury and bleeding BARC 3-5.
 
Additional safety endpoint is the cumulative occurrence of periprocedural myocardial infarction.
 
Finally, the last aim of the AIR-STEMI trial is to assess the cost-effectiveness of the Angiography-derived FFR strategy over conventional angiography.

Study design	AIR-STEMI is a comparative effectiveness study. Participants will be recruited following successful primary PCI and randomized in a 1:1 fashion to an AIR or ANGIO strategy.
Number of participants	1 800
Trial Location	Approximately 20 Italian sites

Inclusion criteria	
 1. STEMI with indication to invasive management (primary PCI) AND 2. Multi-vessel disease defined as at least one non-culprit coronary artery lesion at least 2.5 mm in diameter deemed at visual estimation with a diameter stenosis % ranging from 50 to 99% AND 3. Successful treatment of culprit lesion

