4.4 Exploratory endpoints

- Quality of life measured with EQ-5D quality of life scale
- Angina symptoms control measured with Seattle Angina Questionnaire (SAQ) Frequency scale
- Quality Adjusted Life Years (QALYs)
- Cost effectiveness and cost utility

[figure not shown]
- Number of repeated procedures during index hospitalization

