5.2 Study flow chart

5.3 Screening

All patients undergoing CAA because of STEMI must be screened for eligibility. Patient’s eligibility must be assessed after the evidence of multivessel disease at CAA amenable for PCI with a clear culprit lesion. Successful culprit lesion treatment must be obtained in all patients before randomization. Screening, eligibility and randomization must be performed within 48 hours from the primary PCI and successful treatment of culprit lesion. After eligibility is confirmed, written informed consent must be obtained prior to randomization. Key baseline patient characteristics (i.e., inclusion/exclusion criteria, demographics, medical history, details of cardiovascular anatomy, ECG and laboratory test results) will be recorded on the electronic Case Report Forms (eCRF). All CAA from the initial qualifying PCI as well as all functional assessments will be collected and forwarded to an angiographic core lab for further assessment.

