8.8 Quality of life, Physical performance and Economic assessments

The Seattle Angina Questionnaire and the EQ-5D questionnaire will be used to measure quality of life. Short physical performance battery (SPPB) will be used for physical performance evaluation. In addition, costs will be collected during the course of the study, including medical and resource utilization (including medication and cardiac procedures), re-hospitalizations and emergency room visits.

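### The text schedules EQ-5D and SAQ only at 12 months and 5 years, so QALYs and cost utility would rest on an assumed utility path

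*Protocol*

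**What the plan says.** **What is promised.** The synopsis lists among its secondary efficacy endpoints "iv) Quality Adjusted Life Years (QALYs"), and its endpoint table repeats QALYs as secondary alongside EQ-5D, the EQ-5D VAS and SAQ. Section 4.4 lists EQ-5D, SAQ and QALYs as exploratory, together with "Cost effectiveness and cost utility". The synopsis also states that "the last aim of the AIR-STEMI trial is to assess the cost-effectiveness of the Angiography-derived FFR strategy over conventional angiography".

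**What is scheduled.** Section 7.7 gives the only timing in the text: "quality of life (EQ-5D) will be assessed at the 12-month and 5 year-follow-up visit". That sentence also covers SAQ. An earlier contact exists, since "routine clinic follow-up will occur at 1 month" by telephone or clinic visit, but the content common to all contacts is limited: "At each visit, clinical outcomes, compliance with medical therapy and smoking cessation, will be assessed". Section 5.3 describes the baseline record as "Key baseline patient characteristics (i.e., inclusion/exclusion criteria, demographics, medical history, details of cardiovascular anatomy, ECG and laboratory test results"), with no quality-of-life item. Section 8.8 says that "The Seattle Angina Questionnaire and the EQ-5D questionnaire will be used to measure quality of life" and gives no time points; it adds that costs are collected throughout the study.

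**When follow-up is cut.** Section 9.1 censors all patients when the last one enrolled reaches 1 year.

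**The concern.** A QALY is the area under a patient's utility curve over time, so it needs a starting value and enough later values to trace the path. The text supplies one value in the first year, at its end.

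The protocol gives reasons to expect some difference between strategies early on. Sections 2.8 and 3 argue that a negative functional assessment spares the patient a second procedure. Sections 7.2 and 7.3 place non-culprit revascularization within the index hospitalization. The primary safety endpoint in section 4.3 is kidney injury and BARC 3-5 bleeding, and the creatinine criteria for kidney injury in section 8.7 run over 48 hours and 7 days.

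Under section 8.8 the costs of that period would be observed while its utilities would not, so the two halves of a cost-utility ratio would rest on different evidence. An analysis plan written later cannot recover questionnaires that were never given.

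**Working it through.** The protocol states no QALY figure, so there is none to reproduce. The check is a count of utility values, then an illustration.

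**1. Planned EQ-5D values by time point**

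| Time point | Contact in the protocol | EQ-5D in the text |
|---|---|---|
| Before randomization | Yes (5.3) | Not listed |
| 1 month | Yes (7.7) | Not listed |
| 12 months | Yes (7.7) | Yes |
| 24, 36, 48 months | Yes (7.7) | Not listed |
| 60 months | Yes (7.7) | Yes |

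**2. Values available at the cut.** Section 9.1 gives follow-up of 12 to 22 months. Adding its recruitment period of 20-22 months to the final 12 months gives 32-34 months for the first patient. Both maxima are below 60, so the result does not depend on which applies:

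- survivor: 1 value (month 12);
- death before month 12: 0 values, so the time lived before death has no measured utility.

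Even at 5 years a survivor would have two values, 60 - 12 = 48 months apart, and still none in the first year.

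**3. Dependence of a one-year QALY on the missing values.** The protocol gives no utilities, so all of these are assumptions. Let u0, u1 and u12 be utility at baseline, 1 month and 12 months, with u12 = 0.85.

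- Two points: (u0 + u12)/2. For u0 from 0.40 to 0.85 this is 0.625 to 0.850.
- Three points: (u0 + u1)/2 × 1/12 + (u1 + u12)/2 × 11/12. With u0 = 0.40 and u1 = 0.65 this is 0.044 + 0.6875 = 0.731. With both at 0.85 it is 0.850.
- Month 12 alone: no area is defined. Carrying 0.85 back to day 0 gives 0.850 whatever the early course.

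**4. Dependence of an arm difference.** With equal baselines, the three-point formula reduces to d1/2 + (11/24) × d12, where d1 and d12 are the arm differences in utility at 1 and 12 months. Take d12 = 0.02:

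| d1 | Three-point QALY difference | Month 12 only: equal baseline, straight line | Month 12 only: carried back |
|---|---|---|---|
| -0.05 | -0.025 + 0.0092 = -0.016 | 0.010 | 0.020 |
| 0 | 0.009 | 0.010 | 0.020 |
| +0.05 | 0.025 + 0.0092 = 0.034 | 0.010 | 0.020 |

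The two single-value methods differ by a factor of two and cannot respond to anything before month 12. The width of the three-point range partly reflects linear interpolation, which spreads the 1-month difference over the next 11 months. A difference of 0.05 confined to the first month is worth only 0.05 × 1/12 = 0.004.

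**The case against.** **The schedule may be fuller than section 7.7.** That section starts after discharge, so it does not deal with baseline, and it gives no time point for the physical performance battery or the resource-use data that section 8.8 requires. The baseline list in section 5.3 covers key characteristics and need not be complete. Figures accompany section 7.7 and the synopsis schedule, and their content is not visible in the text; one may show EQ-5D at other times. This stands as a limit: the finding is about what the text schedules. If a figure shows more, it and section 7.7 must be reconciled.

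**A reader might infer that QALYs cannot be computed.** The documents do not support that. A common baseline with a straight path, or mapping from recorded events, would yield a number. Nor does any passage fix the QALY horizon at the primary cut. What remains is that the number would depend on an assumption that the planned data cannot test, and a 5-year horizon leaves the first year equally unobserved.

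**A reader might infer that a missing baseline biases the comparison.** It does not. Allocation is randomized, and chance imbalance is already part of the standard error. Baseline adjustment gains precision.

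**A reader might infer that the strategies differ most in the first month.** The documents do not establish this. Section 2.6 attributes the one-year benefit in the cited angiography-derived FFR trial to fewer infarctions and ischaemia-driven revascularizations, without placing it in month 1. The supportable claim is that any early difference would go unmeasured.

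**Importance.** Section 4.4 makes these endpoints exploratory, and neither primary endpoint nor the sample size depends on them. That limits the weight of the point.

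**Conclusion.** The point holds as a gap between the stated aims and the scheduled measurements. On the visible text, survivors have one utility value at the analysis cut and patients who die before month 12 have none. The count rests only on sections 5.3, 7.7, 8.8 and 9.1. QALYs and cost utility would therefore rest on an assumed utility path.

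The consequence for the QALY difference cannot be sized from the documents. Under the utilities assumed above, the sign could change, but a brief early difference that resolves within a month would matter little. The same gap leaves SAQ without a baseline. The primary efficacy and safety conclusions are untouched. This is an inexpensive improvement worth making, and no threat to the trial's main result.

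**What to change.** 1. In section 7.7 (and 5.3 for baseline), add EQ-5D with VAS and SAQ after consent and before randomization, at the existing 1-month contact, and at every yearly visit. If a schedule figure already shows these, bring the text into line with it.
2. Compute QALYs from these values, with utility set to 0 from death.
3. Adjust only for the pre-randomization value. A discharge value may serve as a follow-up point but not as the baseline covariate: under sections 7.2 and 7.3 it follows allocated in-hospital treatment, so adjusting for it could remove part of the effect.
4. Give QALYs the same tier in the synopsis and section 4.4.

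**Cost.** The questionnaires are short and no new visits are needed; the 1-month contact may be by telephone. Section 5.3 requires randomization within 48 hours of primary PCI, so the baseline value will reflect the acute infarct state. Patients already enrolled will have no baseline, and their number grows with delay.
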